- All adult subjects over the age of 18 with chronic pain* presenting to the emergency department with exacerbation of their chronic pain as their primary complaint
- Subjects who are willing and able to provide informed consent.
- * Chronic pain defined as greater > 3 months of symptoms and an initial VAS pain score > 70

Exclusion criteria:

History of overt psychosis, severe HTN as defined by SBP > 180 or DBP > 110, unstable angina, CAD, CHF, porphyrias, thyroid disease, seizure disorder, inability to provide informed consent: dementia, non-English/Spanish speakers, subjects in custody, suicidal, or clinically intoxicated.

c) Local Number of Subjects

We look to enroll a total of 106 subjects meeting the study criteria.

Protocol Modification 4/24/2018:

We are requesting the enrollment of an additional 10 subjects to the protocol. We initially asked to enroll 96 subjects and have thus far enrolled 80 and the recruitment has continued on schedule. In recent discussion with our statistician and co-investigator, [name], the original group size analysis of 96 (32 in each of three groups) did not account for potential loss of data or subjects withdrawing from the study and we should have asked initially for 106 subjects with the expectation of a 10% loss of data due to incomplete records or withdrawal of subjects in the study.

Rev. 04/24/2018

d) Study-Wide Number of Subjects*

This is a single center study done at the Harbor UCLA Emergency Department

e) Study Timelines*

Duration of an individual subject's participation in this study is 1 emergency department visit and one follow-up phone contact 24-48 hours after discharge from Emergency Department.

The estimated date for the start of enrollment of subjects will be September 2015, and it will be continued till the enrolled subjects' number reach the goal of 106.

f) Study Endpoints*

Primary endpoint: To compare pain relief between the 3 treatment groups as measured by the VAS. A decrease of at least 20mm on the VAS will be considered "significant" pain relief (20)

Secondary endpoint:

- (a) To compare total dosage of IV hydromorphone needed as rescue therapy to achieved adequate pain relief
- (b) To assess the risk for complications of sub-dissociative dose ketamine

g) Procedures Involved in the Human Research*

- 1. The informed consent process will be initiated by investigators in the emergency department.

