- 2. All potential subjects will be informed that participation in the study could lead to a positive urine drug test that could remain positive for up to a month after the conclusion of the study.
- 3. Female subjects of child bearing age, will have a pregnancy test performed prior to enrollment; any subjects who are pregnant will be excluded from this project.
- 4. Each subject will be asked to grade his/her pain severity on a 100mm non-hatched visual analog scale (VAS) ranging from 0 (no pain) to 100 (worst, maximum pain).
- 5. Each subject will be asked to fill out a baseline pain questionnaire
- 6. Each subject will be placed on monitors for continuous pulse oximetry, Heart Rate, Respiratory Rate, and blood pressure every 5 minutes for the duration of the study of one hour and longer for any patient who needs continued care. The patients temperature will be taken prior to the start of the protocol..
- 7. Each subject will have an intravenous catheter placed.
- 8. Each subject will be sequentially assigned to one of three treatment groups, based on a computer-generated randomization schedule, to receive an intravenous infusion of sub-dissociative Ketamine (0.25mg/kg), sub-dissociative dose Ketamine (0.5mg/kg), or an equal amount of normal saline.
- 9. All medications will be prepared by an emergency department pharmacist and all study medication IV bags will be identical in appearance and will be administered by the emergency Page 4 of 11

Rev. 04/24/2018

department nurse caring for the patient who will be blinded to the study drug.

- 10. Each subject will receive lightly tinted sunglasses to wear during the duration of the study to minimize bias as ketamine can evoke a tell-tale short-lived nystagmus
- 11. Each subject will receive the study medication over a 20 minute period via an automated pump. At this point, the subjects will be asked to rate their pain on a VAS and asked if they need additional pain medication that will consist of intravenous hydromorphone with the dose and frequency determined by the discretion of the treating physician and documented on the data collection sheet.
- 12. After 1 hour the subject will again be asked to grade his/her pain on a VAS. Additionally, they will be asked if they experienced any other adverse effects over the treatment period, specifically: rash, hallucinations, anxiety, disorientation, burning at the injection site.

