- 13. Subjects will be asked if they require additional pain relief. Those who request further pain relief will be administered hydromorphone IV, the dosage and frequency will be at the discretion of the treating physician. Total hydromorphone administration will be documented on the data collection sheet.
- 14. All subjects will receive a follow-up phone call from one of the investigators between 24 48 hours after their visit to the Emergency Department to gauge the extent of their continued pain through the use of a Pain Rating Scale. They will also be asked if they suffered any untoward effects and if so, will be asked to detail them.
- 15. Any study patient returning to the Emergency Department for any reason will be fully evaluated and the study team will be notified. If there is evidence of any psychotic reaction (persistent or delayed presentation after the administration of the medication, the patients will be treated with benzodiazepines (shown to be effective in the emergence reaction sometimes seen after dissociative doses of ketamine are used) and a psychiatric consult will be obtained. The medical monitor will also be notified because this would be an adverse event.

h) Data and Specimen Banking*

No data collected for banking purposes.

i) Data Management *

Descriptive statistics will be used. Tests for significance will be conducted using the t test for continuous variables and chi-squared test or Fisher's exact test for categorical variables.

We estimated the sample size needed for the primary end point of significant pain relief as defined by a decrease in the VAS of 20mm. A power analysis based indicated that a sample size of 106 subjects would be required to detect a statistically significant difference with a power of 90% ($\alpha = 0.05$).

Data from the patient examinations will be stored in an excel spreadsheet or compatible REDCAP database after being de-identified of all unique information to the subject. The study source documents (including consent forms, etc.) will be stored in a locked filing cabinet in a locked office only accessible by study investigators. It will be stored until this

Rev. 04/24/2018

study completes. The data will be shared among the principal investigator and coinvestigators. Principal investigator will be responsible for receipt or transmission of the data.

Protocol Modification 4/24/2018:

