We are requesting the enrollment of an additional 10 subjects to the protocol. We initially asked to enroll 96 subjects and have thus far enrolled 80 and the recruitment has continued on schedule. In recent discussion with our statistician and co-investigator, [name], the original group size analysis of 96 (32 in each of three groups) did not account for potential loss of data or subjects withdrawing from the study and we should have asked initially for 106 subjects with the expectation of a 10% loss of data due to incomplete records or withdrawal of subjects in the study.

j) Confidentiality

Confidentiality will be maintained by use of coded data sheets and an enrollment logbook. Data will be stored in a password locked excel data sheet s/REDCAP database. The study source documents (including consent forms, etc.) will be stored in a locked filing cabinet in a locked office only accessible by study investigators. It will be stored until the completion of this study. Only research investigators and research associates will have an access to this data or the room where the data sheets and enrollment logbook is kept.

k) Provisions to Monitor the Data to Ensure the Safety of subjects*

[name], an Emergency Physician not associated with the study but who has an expertise in procedural sedation in emergency department patients will be a Safety Monitor who will review all patient information whether they received placebo or ketamine for both harm and benefit on a monthly basis to determine if the study is safe to continue. [name], is an LAbiomed investigator with significant experience in the conduct of research and possesses the expertise to serve as the Safety Monitor.

l) Withdrawal of Subjects*

Subjects will be withdrawn from the study if they don't complete their Ketamine or normal saline infusion and they will continue to be monitored and treated as necessary if they experience any untoward or unexpected effects from the medication.

10) Risks to Subjects*

Risk of Ketamine

Incidence unknown: Bloody or cloudy urine, bluish lips or skin, blurred vision, chest pain or discomfort, confusion, disorientation, convulsions, cough, increased secretions, dizziness, syncope, tachycardia, hives, itching, facial edema, hallucinations, rash, agitation, anxiety, fatigue, unmasking psychosis

Risk of Sodium Chloride

Common: None Uncommon: Edema

Rare: Congestive Heart Failure from fluid overload

Risk of intravenous catheter insertion

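### The 24–48 h call asks about harms only in general terms, so late neuropsychiatric effects are likely to be under-ascertained, to an unknown degree and similarly in all arms

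*Combined protocol and SAP*

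**What the plan says.** Section 9(g) schedules two questions about harms.

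- **At 1 hour (step 12).** The question covers a set window, "they will be asked if they experienced any other adverse effects over the treatment period", and carries a list: "specifically: rash, hallucinations, anxiety, disorientation, burning at the injection site".
- **At 24–48 hours (step 14).** An investigator telephones every subject, takes a pain rating and asks about harms: "They will also be asked if they suffered any untoward effects and if so, will be asked to detail them". No list is given for this call.

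Section 9(e) describes participation as "1 emergency department visit and one follow-up phone contact 24-48 hours after discharge from Emergency Department", so the call is the only scheduled contact after discharge.

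The plan foresees late effects. Step 15 says what to do "If there is evidence of any psychotic reaction (persistent or delayed presentation after the administration of the medication"; the response is benzodiazepines and a psychiatric consult. Section 10 includes "hallucinations, rash, agitation, anxiety, fatigue, unmasking psychosis" among the ketamine risks, lists confusion and disorientation as well, and gives no incidence for any of them. Section 9(f) makes the risk of complications secondary endpoint (b).

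One safeguard after discharge is stated in step 15: "Any study patient returning to the Emergency Department for any reason will be fully evaluated and the study team will be notified".

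**The concern.** The investigators use named prompts at 1 hour and specify none at the one later contact that could find the delayed reaction they prepare for in step 15. A subject who had a brief hallucination, some hours of disorientation or new anxiety may not think of it as an untoward effect, may not link it to the infusion, or may not volunteer it.

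Two things are at stake. One is the late part of secondary endpoint (b), where both the rate and the contrast between arms would probably come out too small. The other is the individual subject, whose continuing reaction may go unrecognised because nobody asked.

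**Working it through.** **Step 1. Who is asked what, by time of onset (sections 9(e) and 9(g)).**

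| Onset of effect | Asked by name? | Other stated routes |
|---|---|---|
| Up to 1 hour | Yes, step 12 | Monitoring, step 6 |
| After 1 hour, before discharge | No | Continued monitoring if care is needed, step 6; open question at the call |
| After discharge, before the call | No | Open question at the call; return to this ED |
| After the call | No | Return to this ED only |

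The second and third rows are where a prompt at the call would help.

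**Step 2. What this does to endpoint (b).** Let p be the true late rate in an arm, s the share of true late effects that the question elicits, and f the share of unaffected subjects who report one anyway. Then

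recorded rate = p·s + (1 − p)·f.

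If s and f are the same in a ketamine arm (k) and the control arm (c),

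recorded difference = (p_k − p_c)·(s − f).

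So a low s shrinks the difference without favouring an arm. Only when f = 0 are the recorded rate and the recorded difference both exactly s times the truth. Equal s and f are reasonable here: step 14 applies to all subjects, an investigator makes the call, and section 18 says that only the pharmacist knows which drug was given.

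The documents give neither p, s nor f. The following is illustration only, with assumed values, f = 0 and 106/3 ≈ 35 per arm. The chance of recording at least one late case in an arm is 1 − (1 − p·s)^35.

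| True late rate p | s = 0.3 | s = 0.5 | s = 0.9 |
|---|---|---|---|
| 3% | 0.27 | 0.41 | 0.62 |
| 5% | 0.41 | 0.59 | 0.80 |
| 10% | 0.66 | 0.83 | 0.96 |

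Likewise, a true difference of 20% against 5% would be recorded as 15 × 0.5 = 7.5 points at s = 0.5 and 15 × 0.9 = 13.5 points at s = 0.9. The range shows that s could matter. It does not show that it does.

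**Step 3. What a change can still reach.** Section 9(c) gives a target of 106 and 80 enrolled at the modification of 24 April 2018. The earlier plan of 32 in each of three groups implies equal allocation.

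- Remaining: 106 − 80 = 26 at most; 26/106 = 25%.
- On ketamine: 26 × 2/3 = 17.3, about 17. Per arm: 26/3 = 8.7, about 9.
- One-sided 95% upper limit for the late rate if no event is reported: 1 − 0.05^(1/17) = 0.162 for 17 subjects, and 1 − 0.05^(1/9) = 0.283 for 9.

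Prompted data on the remaining subjects cannot give a precise rate.

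**The case against.** **An open question followed by a request for detail is a legitimate way to collect harms, and nothing in the documents compares it with a list.** This stands as far as size goes. The direction is a methodological inference, and the protocol's own use of a list at 1 hour only supports it indirectly.

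**Subjects are not naive at the call.** Under section 15 they must describe some risks in their own words before enrolling, and they have heard the step 12 terms at 1 hour. Section 9(b) also excludes a history of overt psychosis, suicidality and clinical intoxication. These facts make the likely loss smaller. They do not mean that a later effect is asked about.

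**The documents do not show that late effects are common.** This is also true. Section 10 gives no incidence for its whole ketamine list and says nothing about late onset. Step 15 links the emergence reaction to dissociative doses, which this trial does not use.

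**Prompts can add noise.** Section 10 accepts that rating pain may itself cause anxiety, and hydromorphone rescue is available in every arm. Prompting may raise f as well as s. This is a real cost.

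Three stronger readings are tempting, and the documents support none of them.

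- *The 80 subjects already enrolled were never prompted at the call.* Only the protocol wording is available. The call form is not shown and may have contained prompts.
- *The open question biases the comparison.* The same question goes to all arms from a blinded caller, so the expected effect is dilution.
- *The monitor hears only of psychosis.* Step 15 attaches notice to a psychotic reaction, but its reason, "The medical monitor will also be notified because this would be an adverse event", can be read more widely. Section 9(k) has a Safety Monitor review all patient information monthly. The text does not say whether the medical monitor and the Safety Monitor are one person, and institutional reporting is not shown. That is missing detail, not a demonstrated gap, and it forms no part of this point.

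**Conclusion.** The point holds in a limited form. As the protocol is written, neuropsychiatric effects that start after the first hour are not asked about by name at any scheduled contact, although step 15 anticipates them. They are likely to be under-ascertained, similarly in all arms and to a degree that the documents do not allow anyone to size. The effect falls on the late part of secondary endpoint (b) and on individual safety; the primary VAS endpoint is unaffected.

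This rests on three assumptions: that the call follows the wording of step 14, that an open question elicits fewer such effects than a named one, and that s and f do not differ by arm. If the call form already contains prompts, the protocol text merely needs to say so. This is a cheap improvement for the investigators to consider, and it does not threaten the trial's main conclusion.

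**What to change.** In section 9(g), step 14, for the remaining subjects:

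1. Keep the open question, and ask it first, so that the answer stays comparable across everyone reached by the call.
2. Then ask by name about hallucinations, anxiety and disorientation, the neuropsychiatric items of step 12. Agitation and confusion, both in section 10, may be added. For each positive answer record when it began and whether it is ongoing.
3. In the analysis, report the open-question answers for all subjects reached. Report the prompted items separately, with the subjects documented as having been asked them as the denominator.

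The cost is a sentence or two of protocol text and three to five short questions on a call that is already planned. The downsides are a slightly longer call, some extra background reports (anxiety above all), and prompted answers from a minority of subjects, at most 26 unless earlier call records show that prompts were used. Effects that begin after the call would still depend on a return to this ED.

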1) Protocol Title

Subdissociative Dose Ketamine for Treatment of Acute Pain in Subjects with Chronic Pain: A Randomized Controlled Trial

2) HSC Review History

This protocol has not been reviewed by any external HSC.

3) Investigator [name], MD [name] [name], MD [name] [name] [name]

4) Objectives*

This is a prospective, randomized, physician and subject blinded controlled clinical trial. This will be conducted to determine whether sub-dissociative dose Ketamine can improve pain control in subjects with chronic pain syndrome presenting to the emergency department with exacerbation of their chronic pain. We also aim to determine whether use of SDDK can reduce the amount of subsequent opioid pain medications required for adequate pain relief in this subject population. We hypothesize that there will be a statistically significant decrease in pain using SDDK versus placebo and subjects will require overall less opioid pain medications for adequate pain relief.

5) Background*

Pain management is a significant issue for many subjects presenting to the Emergency Department (ED) as increasing numbers of subjects present with this complaint. In the ED, treatment of acute pain is a primary concern both for the provider and the subject; recent data suggest that visits for pain-related complaints are rising (1). Subjects with chronic pain account for 12-16% of total ED visits (2,3) with 7% of subjects with chronic pain presenting multiple times (4). Both the Department of Health and Human Services (HHS) and the Institute of Medicine (IOM) have identified pain as a significant public health problem in the United States (5). Currently, the vast majority of painful conditions within the ED are treated with either opioid or non-steroidal anti-inflammatory drug (NSAID) analgesic medications. Treatment of chronic pain syndromes in the ED can be particularly challenging, since many subjects with these conditions are tolerant to the effects of opioids and NSAIDs and it can therefore be difficult to control their pain exacerbations adequately in the emergency department solely with these medications

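### The primary endpoint compares three groups on the VAS, but the plan fixes no contrast, overall test, outcome form or rating time, so the primary result has no defined family-wise error rate

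*Combined protocol and SAP*

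**What the plan says.** Section 9(f) states the primary endpoint: "To compare pain relief between the 3 treatment groups as measured by the VAS". It adds that a fall of 20 mm or more counts as significant relief. The three groups in section 9(g), step 8, are two ketamine doses and saline.

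The inferential plan is one sentence in section 9(i): "Tests for significance will be conducted using the t test for continuous variables", followed by "chi-squared test or Fisher's exact test for categorical variables". The sizing paragraph there refers to "the primary end point of significant pain relief as defined by a decrease in the VAS of 20mm" and gives 90% power at α = 0.05, the only error rate in the document. Section 9(c) puts the group size before allowance for losses at 32 per arm.

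Two post-dose ratings are planned. After the 20-minute infusion (step 11), "the subjects will be asked to rate their pain on a VAS and asked if they need additional pain medication". Step 12 adds: "After 1 hour the subject will again be asked to grade his/her pain on a VAS". Neither is called primary.

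Section 4 hypothesises that "there will be a statistically significant decrease in pain using SDDK versus placebo". It does not say whether the two doses are pooled, tested separately or tested in order.

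**The concern.** A two-sample t test compares two groups. It cannot answer a three-group question unless two arms are pooled or the test is repeated, and the plan specifies neither. Repeating it at 0.05 without a gate or adjustment raises the chance of at least one false positive above 0.05.

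Two further choices are open. The outcome may be VAS change in millimetres or the 20 mm responder classification, and the rating may be end of infusion or 1 hour. If these are settled after the data are seen, the 0.05 used for sizing no longer describes the error rate of the primary claim.

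**Working it through.** **Inputs from the document.** Three arms, 32 per arm, α = 0.05, 90% power, a 20 mm threshold, two post-dose ratings.

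**Assumptions.** Two-sided tests (sidedness is not stated), normally distributed VAS change, equal variances and no true effect unless stated. Between-rating correlations of 0.5 to 0.9 and responder rates of 30–60% are also assumed; the document gives neither.

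**The plan's own figure.** The allowance for losses reproduces: 96/(1 − 0.10) = 106.7 and 96 × 1.10 = 105.6, against the stated 106. The 32 per arm cannot be reproduced, because no SD or responder rates are given. If it came from a two-group comparison of a 20 mm mean difference, the normal approximation gives

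SD = 20 / [(1.960 + 1.282) × √(2/32)] = 20 / 0.810 = 24.7 mm.

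The exact t calculation gives 24.3 mm. This affects only the power costs, not the error rates below.

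**VAS change, one rating, unadjusted t tests.**

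- Each dose against saline (two tests sharing a control), large-sample: 1 − ∫ φ(g)[Φ(1.96√2 + g) − Φ(−1.96√2 + g)]² dg = 0.091. Simulation at 32 per arm: 0.090–0.091.
- All three pairs: the probability that the studentized range of three means exceeds 1.96√2 is 0.122. Simulation: 0.122–0.123.
- Treating the tests as independent would give 1 − 0.95² = 0.0975 and 1 − 0.95³ = 0.143. Both are too high, because the comparisons share arms.

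**VAS change, either rating may count (simulated).**

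| Correlation between ratings | Two tests per rating | Three tests per rating |
|---|---|---|
| 0.5 | 0.161 | 0.213 |
| 0.7 | 0.149 | 0.197 |
| 0.9 | 0.125 | 0.167 |

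**Responder outcome, one rating (exact enumeration, common rate 0.3 to 0.6).**

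| Test | Two doses against saline | All three pairs |
|---|---|---|
| Fisher's exact | 0.052–0.061 | 0.072–0.083 |
| Uncorrected chi-squared | 0.093–0.108 | 0.124–0.144 |

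A single Fisher test runs at only 0.028–0.033, which is why repeating it inflates little.

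**Readings that hold about 5%.** Pooled ketamine against saline by t test: 0.050. Single 3×2 chi-squared test: 0.051–0.054. Overall F test followed by pairwise t tests only if significant: 0.050.

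**Outcome form also open.** If a t test or a Fisher test, at either rating, on any of the three pairs could count, simulation at an assumed 50% responder rate gives about 27%, 25% and 22% at correlations 0.5, 0.7 and 0.9.

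**The case against.** The strongest reply is that the t-test sentence may not govern the primary endpoint. The sizing paragraph describes that endpoint by the 20 mm decrease. Read as yes/no, it calls for chi-squared or Fisher's exact, and a 3×2 chi-squared test is already a three-group test that holds about 5%. Section 4's ketamine-against-placebo hypothesis likewise fits one pooled test at 5%.

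This limits the size of the problem, and that much stands: the 9–12% belongs to the continuous branch. It does not remove the gap. Section 9(f) words the endpoint as pain relief measured by the VAS, which also fits a continuous analysis. Nothing says that the categorical test is 3×2 rather than pairwise, and pooling is nowhere mentioned. A compliant reading that the plan does not commit to cannot control error.

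A reader might infer that the sponsor intends unadjusted tests. The document does not say so; it is silent. Nor does it say that significance at either rating, or in either outcome form, would be claimed as the primary result, so the higher figures show what the wording leaves possible, not what was planned.

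**Conclusion.** The concern holds as under-specification with a material consequence on some readings, and it should be corrected. With t tests on VAS change, the family-wise error that the wording permits runs from about 5% (one pooled test) to about 21% (three pairs, either rating, correlation 0.5). That range covers contrast and rating time for t tests only. With outcome form open as well, the upper end is about 22–27% under the stated assumptions. For two pairwise Fisher tests on the responder outcome at one rating, the inflation is small.

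Two stronger conclusions are not supported. The primary analysis cannot be said to carry a 9–12% error rate outright, because that figure is conditional on separate unadjusted t tests. Nor is the sample size shown to be wrong: its inputs are missing, which prevents a check but does not refute it.

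**What to change.** Before unblinding, amend section 9(i) to name one primary outcome form, one primary VAS rating and one error-controlled three-group test at two-sided 0.05. The end-of-infusion rating is one candidate, because step 11 lists it before the question about rescue medication. All other VAS comparisons should be labelled secondary.

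- **If VAS change is primary:** replace the t test with an overall three-group F test and make pairwise comparisons only if it is significant. With exactly three groups this gate is sufficient: if one arm truly differs from two equal arms, only one true null pair remains. Baseline-adjusted ANCOVA is a separate, optional gain that multiplicity does not require.
- **If the 20 mm responder outcome is primary:** use a single 3×2 chi-squared test as the gate.
- **Also acceptable if stated in advance:** a fixed order of dose-against-saline tests, a Dunnett-type test, or a pooled ketamine-against-saline test.

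The change needs a few sentences and no extra subjects or data. The cost is some power for a single dose-against-saline comparison. For unadjusted VAS change and a true 20 mm difference, the F-test gate lowers power from 90% to 83–88%, depending on the other dose's effect (0 to 20 mm); a Dunnett-type test gives 85%. These figures assume that the 32 per arm came from a two-group t test for a 20 mm difference with SD about 24.3 mm; the document states neither. With the F-test gate, power falls from 98% to 95–97% at SD 20 mm, and from 75% to 63–69% at SD 30 mm. The power cost of the responder option was not computed.

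### The primary VAS analysis is left open (continuous or 20 mm responder, end of infusion or 1 hour), with no baseline covariate and no error control over the ketamine-saline contrasts; a dated amendment naming an ANCOVA with Holm is a cheap, minor-to-moderate improvement

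*Combined protocol and SAP*

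**What the plan says.** **Endpoint.** Section 9(f) gives the primary aim as "To compare pain relief between the 3 treatment groups as measured by the VAS". It then adds a threshold: "A decrease of at least 20mm on the VAS will be considered" significant relief. Section 4 states the hypothesis as "We hypothesize that there will be a statistically significant decrease in pain using SDDK versus placebo". Section 9(i) sizes the trial on "the primary end point of significant pain relief as defined by a decrease in the VAS of 20mm".

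**Tests.** Section 9(i) says: "Tests for significance will be conducted using the t test for continuous variables and chi-squared test" or Fisher's exact test for categorical variables. It does not say which test serves the primary endpoint. No covariate model, named contrast or multiplicity rule appears, although step 8 of section 9(g) sets up three arms.

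**Readings.** VAS is recorded before treatment (9(g) step 4; section 9(b) requires a score above 70), after the 20-minute infusion (step 11) and at 1 hour (step 12). Neither post-infusion reading is named as primary. Step 11 reads: "At this point, the subjects will be asked to rate their pain on a VAS and asked if they need additional pain medication". The 1-hour VAS may therefore follow hydromorphone.

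**Size.** Section 9(c) gives 32 per group, 96 in all, raised to 106 for 10% loss. Section 9(i) states 90% power at alpha 0.05.

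**The concern.** Three choices are left to the analyst: the type of endpoint, the time point and the contrasts. Each can be made after the data are seen, and each can change the result.

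The options also differ statistically. A responder test ignores how far each subject is from the 20 mm line. A change score uses baseline with a fixed coefficient of one, and a raw-VAS t test does not use it at all. Two ketamine-saline tests, each at 0.05, carry more than 5% error between them. At 1 hour, the comparison mixes the effect of the study drug with that of any hydromorphone given since step 11.

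**Working it through.** SDs, effects, placebo falls and baseline slopes below are assumptions, because the documents give none. Tests are taken as two-sided.

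**1. The plan's own figure.** The 90% cannot be reproduced: no SD, responder rates, sidedness or comparison is stated. The loss step can be checked: 96 × 1.1 = 105.6, so 106 (96 / 0.9 = 106.7 is close).

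**2. Does 32 per group reveal the intended endpoint?** It does not.
- Continuous: two-sample t test, 62 df, noncentrality d√(32/2). Power of 90% needs d = 0.823, so a 20 mm effect implies SD = 20 / 0.823 = 24.3 mm.
- Responder: 20% versus 58% gives 90.3% by exact enumeration of the chi-squared test.

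**3. Value of the covariate.** Let follow-up = b × baseline + noise with SD σ, and take baseline as uniform on 70 to 100, so its SD is 30/√12 = 8.66 mm. The variances are:
- change score: σ² + (1 − b)² × 8.66²
- raw VAS: σ² + b² × 8.66²
- ANCOVA: σ², with one degree of freedom less

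Pairwise power at 0.05, σ = 24.3 mm, 20 mm effect:

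| Slope b | ANCOVA | Change score (SD) | Raw VAS (SD) |
|---|---|---|---|
| 0 | 90.0% | 86.3% (25.8) | 90.0% (24.3) |
| 0.5 | 90.0% | 89.1% (24.7) | 89.1% (24.7) |
| 1 | 90.0% | 90.0% (24.3) | 86.3% (25.8) |

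The gain is 0 to 3.7 points against either alternative. Three-arm simulation with Holm (both doses 20 mm, slopes 0.5 and 1, SD 18 to 30 mm) gives -0.8 to +1.3 points against a change score and -0.1 to +3.4 against raw VAS. Together these give about -1 to +4. If the doses work by 10 and 20 mm, the gain over raw VAS reaches 4.9 points, part of which comes from pooling variance over three arms. In the table, the correlation of baseline with follow-up is at most 0.34. At a correlation of 0.5, ANCOVA would have about 96% where a raw-VAS t test has 90%.

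**4. Responder test, sized at 90% as stated.** With a normally distributed fall, d is the difference between the normal quantiles of the two responder rates:

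| Rates | d | SD for 20 mm | Chi-squared / t at 0.05 | Chi-squared / t at 0.025 |
|---|---|---|---|---|
| 0.20 vs 0.58 | 1.04 | 19.2 | 90.3 / 98.4% | 84.7 / 96.8% |
| 0.30 vs 0.69 | 1.02 | 19.6 | 91.0 / 98.0% | 86.0 / 96.0% |
| 0.40 vs 0.79 | 1.06 | 18.9 | 91.6 / 98.7% | 86.5 / 97.2% |
| 0.50 vs 0.87 | 1.13 | 17.8 | 91.7 / 99.3% | 85.7 / 98.5% |

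The gain is 7 to 8 points at 0.05 and 10 to 13 at 0.025. The comparison is with a plain t test, so it comes from not dichotomising.

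**5. Two contrasts.** Independent tests would give 1 − 0.95² = 9.75%. Sharing the saline arm lowers this to about 9.0% by simulation at 32 per arm. ANCOVA with Holm gives 4.4 to 4.7%. The price at SD 24.3 mm is that power at the first Holm step (0.025) is 84% instead of 90%. Across both Holm steps, with both doses at 20 mm, each contrast has 84 to 88%.

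**6. The 1-hour reading.** As an illustration, suppose 50 to 90% of subjects below 20 mm relief receive hydromorphone, adding 15 to 35 mm, at SD 24.3 mm. A t test on the observed VAS, ignoring rescue, then ranges from 14 points worse to 17 points better than a responder test counting rescue as failure.

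**The case against.** **The covariate is not the main gain.** The t test already listed in 9(i) captures nearly all the benefit over a responder test. This stands: ANCOVA adds little to a change score, and the point should not be sold as a large gain from baseline adjustment.

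**A large loss of power from a responder test.** A reader might put SD 24.3 mm into the responder test, find 63 to 77% power against 90% for the t test, and conclude that the trial is underpowered. The documents do not support this. That SD was solved by supposing a t test had 90%. If 9(i) sized a responder test at 90%, the matching SD is about 18 to 20 mm, and the figures in step 4 apply. Larger gains arise only if the responder test was not in fact powered at 90%.

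**Baseline ignored altogether.** A reader might infer this too, but any decrease subtracts baseline. Only its use as a covariate is missing.

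**A responder endpoint is legitimate.** This stands. If it was intended, ANCOVA answers a different question, about mean pain rather than the proportion relieved, and the sponsor may prefer the original question.

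**More than wording.** This also stands. The amendment chooses the primary variable, time and test after 80 subjects were enrolled, so it must be dated and made before unblinding. The advantage is also claimed only for the end-of-infusion reading; at 1 hour it can reverse.

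**Conclusion.** The point holds in a limited form. The text leaves endpoint type, primary reading and contrasts open, and the listed tests provide neither a baseline covariate nor error control over two ketamine-saline comparisons. That much rests on the documents alone.

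The size is modest. Unadjusted testing of both contrasts carries about 9% family-wise error. The covariate is worth about -1 to +4 points of power against a change score or raw VAS at baseline slopes 0 to 1, and more against raw VAS if the correlation is stronger. A continuous analysis is worth about 7 to 8 points at 0.05 (10 to 13 at 0.025) over a responder test sized at 90%. These figures assume 32 per arm, normally distributed falls, a 20 mm effect and no rescue before the reading. They do not show that the trial falls short of its stated 90%, because its sizing inputs are not given. This is a cheap improvement, minor to moderate, held with medium confidence.

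**What to change.** By a dated amendment to 9(f) and 9(i) before unblinding, state one primary analysis:

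- **Variable and time:** VAS in mm at the end of the 20-minute infusion (step 11), the reading taken when hydromorphone is first asked about.
- **Model:** ANCOVA with treatment group and baseline VAS, reporting adjusted mean differences with 95% confidence intervals.
- **Contrasts:** each ketamine group versus saline, with Holm at an overall two-sided 0.05. If only one contrast is to be primary, name it and test it at 0.05.
- **Secondary:** the proportion with a fall of at least 20 mm, and the 1-hour VAS.

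If the sponsor keeps the responder endpoint or the 1-hour reading as primary, the amendment should say so and state how hydromorphone given between the readings is handled in the analysis.

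**Cost:** no added patients, visits or measurements; one degree of freedom for the covariate; and first-step power per contrast of about 84% instead of 90% at SD 24.3 mm. That last cost comes from having two primary contrasts, and a responder test would also pay for sharing alpha. The 20 mm result is still reported.
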